## 1.0 Objectives / Specific Aims

Parkinson's disease (PD) is a movement disorder characterized by resting tremor, slowness of movement (bradykinesia), muscle rigidity and postural imbalance. These motor symptoms arise predominantly from abnormal activity in the basal ganglia-thalamocortical circuit. Deep brain stimulation (DBS) of the basal ganglia was developed as a surgical treatment for PD patients who have become refractory to medical therapy. In a recent study (Rowland et al, 2015 – pdf uploaded in General Comments section), we compared movement dynamics in two types of patients undergoing DBS surgery – PD and essential tremor (ET) patients – performing the same motor task. We found that motor cortical activation, i.e., reduction of beta oscillations, in PD patients preceded that of ET patients, beginning during motor preparation before movement had begun. This finding demonstrates a compensatory strategy that can be used by motor networks in the brain to augment voluntary movement and offers a potential biomarker that may be used in future forms of neuromodulation to improve PD symptoms.

Approximately 2-5% of patients undergoing DBS will experience a surgery-related complication. The most serious of these is hemorrhage and stroke due to penetration of the brain parenchyma by the DBS electrode to reach the basal ganglia. One alternative form of stimulation that has been shown to have modest benefit in some patients with PD is transcranial direct current stimulation (tDCS), in which electrodes are placed on the scalp and deliver current noninvasively to the motor cortex. Although the results from tDCS are promising, our **central hypothesis** is that this form of stimulation produces inconsistent results in PD patients because a detailed understanding of motor cortical response to tDCS is lacking. To address this problem, we propose performing direct measurement of motor cortical oscillations in response to tDCS to determine how these signals might be used in improving this noninvasive therapy for treatment of PD-related motor symptoms. Progress in treating PD symptoms noninvasively might also lead to similar treatment strategies for all movement disorder patients undergoing DBS, including ET and dystonia patients.

In our previous study (Rowland et al, 2015), PD patients undergoing DBS surgery performed an arm-reaching task during subdural electrocorticography (sECOG) recording of beta (13-30 Hz) and broadband gamma (70-200 Hz) oscillations, showing modulation related to both movement preparation and execution. However, the exact frequency bands and phases of movement modulated by tDCS remain poorly understood. Patients undergoing DBS surgery for PD and ET are usually awake and, furthermore, the procedure provides access to primary motor cortex. Thus, during awake, frameless DBS surgery, responses in motor cortex can be measured safely in behaving subjects. Patients undergoing DBS surgery for dystonia are usually asleep, offering an opportunity to compare how tDCS affects motor cortical oscillations when patients are not engaged in a motor task. In some instances, PD and/or ET patients also request to be asleep during DBS surgery, allowing comparison between awake and asleep populations.

We will investigate the effect of tDCS on motor cortical oscillations in patients undergoing DBS surgery through the following specific aims:

**Aim 1. Quantify the change in primary motor cortical (PriMC) oscillations during cued arm reaching in relation to tDCS activation.** Question: Does tDCS differentially modulate movement preparation vs movement execution? In this aim, we will record beta and broadband gamma oscillations in PriMC in awake patients undergoing frameless DBS surgery using an

sECoG electrode while applying high-density tDCS focused on PriMC. Patients will be videotaped in order to correlate movement dynamics with ECoG signals. *We hypothesize that cortical beta and broadband gamma spectral power changes will be enhanced more so during movement preparation than execution following anodal tDCS activation.*

**Aim 2. Quantify the change in PriMC oscillations during framed DBS (either awake or under general anesthesia) in relation to tDCS activation.** Question: Does tDCS modulate motor cortical oscillations in the absence of movement? In patients undergoing framed DBS (either awake or asleep), cortical oscillatory changes will be recorded during application of tDCS using different amplitudes, durations, polarities, lateralities, and stimulation patterns. *We hypothesize that cortical beta and broadband gamma spectral power will be modulated using different amplitudes, durations, polarities, lateralities, and stimulation patterns in the absence of movement.*

This project has been awarded grant funding through a South Carolina Clinical and Translational Research Institute (SCTR) K12 award (#UL1 TR001450).

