#### **Procedure steps**

In brief, standard of care DBS surgery involves drilling a 1.4 cm burr hole in the skull and implanting an electrode that penetrates the brain parenchyma into the basal ganglia or thalamus. For patients participating in this research, all surgical procedures will be the same, with the exception of the research-dedicated steps: 1) the sECoG electrode will be inserted using the same burr hole drilled previously but will remain on the surface of the brain and will not penetrate the brain, 2) the tDCS electrodes will be applied to the scalp (awake patients with frameless DBS will also be outfitted with virtual reality goggles), 3) the tDCS electrodes will be activated (awake, frameless DBS patients will perform up to two motor tasks before, during and/or after stimulation and videotaped during the task); the task will not be performed if the patient is awake but has a stereotactic headframe on or is asleep under general anesthesia, 4) in all patients the surgical site will be photographed to capture the tDCS montage as well as any other aspect of the setup relevant to offline reconstruction of behavioral and physiology data), 5)

all research-related equipment will be removed from the surgical field, 6) the subject will proceed to have the DBS surgery as per standard of care.

DBS surgery is reimbursed by insurers using a Diagnosis Related Group (DRG) model. This means that once a patient is preauthorized by an insurer to undergo DBS surgery, the surgery, hospital stay and all related procedures are bundled together and covered at a fixed cost. Costs related to research activity during this study (20 minutes total) will be charged to a research account and will not result in additional charges to the patient, hospital or the patient's insurer. In a recently published study documenting 200 cases of sECoG insertion during DBS surgery in movement disorder patients and in which all study related procedures took place in 20 minutes or less ('Intraoperative electrocorticography for physiological research in movement disorders: principles and experience in 200 cases', by Panov et al, 2017), **no infections related to the sECoG electrode occurred**. In this study, we will allow 20 minutes total to include setup and breakdown of the study-related equipment.

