## **Step 2: Placement of tDCS electrodes and virtual reality goggles**

We will place the tDCS electrodes onto the patient's scalp which will be previously shaved of all hair (depending on laterality of procedure – either unilateral or bilateral) in accordance with the standard clinical DBS procedure. The electrode array consists of one central electrode and four surrounding electrodes (total of five ring electrodes, each 1 cm in outer diameter, 2 mm thickness). The central electrode will be placed at a location directly overlying primary motor cortex as determined by coordinates generated through neuronavigational software used for DBS electrode trajectory planning. For purposes of sterility, the patient's scalp will be covered with an iodine-impregnated adhesive film per standard of care procedures. The electrodes, which will be sterilized with ethylene oxide prior to the procedure, will be secured in place using additional sheets of this film, which will serve as an additional preventive measure against possible infection. Next, the tDCS electrodes will be connected to a low-current generator placed away from the surgical field and powered by alkaline batteries. The device will be manually controlled by IRB-approved study personnel in the operating room to assist with the procedure. For presentation of visual images for patients who are awake and undergoing frameless DBS, patients will be outfitted with virtual reality goggles (Oculus Rift, Menlo Park, CA). The Oculus system also comes with a hand controller that is held by the patient and tracked in three-dimensional space, serving as a marker of upper extremity movement. Presentation of visual images will be manually controlled by IRB-approved study personnel in the operating room to assist with the procedure.

It is important to note that neither the tDCS nor sECoG electrodes will penetrate the brain at any time. Both electrodes will remain outside the brain itself. The tDCS electrode will remain on top of the scalp; the sECoG electrode will remain underneath the skull and on top of the brain surface (see Figure 1, Step 3). Only the DBS electrode performed for standard of care treatment of PD will penetrate the brain.

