times. If no virtual touch is made at a location for 2 seconds, the blue dot will cycle to the next location automatically. Once the blue dot has cycled 5 times, both the blue and green dots will disappear and the red dot will reappear in the center of the screen (accompanied by an auditory cue) to complete 1 trial. Patients will be instructed to rest quietly when the red dot appears (rest phase). Appearance of the blue dot will signal that the patient is to prepare to move once the green dot appears (movement preparation phase). Patients will be instructed to move at a natural speed. This is to avoid confounding changes in beta and broadband gamma oscillations due to movement speed and force. Patients will be given an introduction to the task and an opportunity to practice several trials in the preoperative area while waiting for surgery to begin. Rest, movement preparation and movement execution will be analyzed as separate epochs. Beta and broadband gamma spectral power during each movement phase (rest, prep and move) will be analyzed separately. In our previous work (Rowland et al, 2015), the entire task took 3 minutes to complete. The entire task will be videotaped and repeated no more than twice. Videotaping will occur using a high-resolution web camera secured to a computer monitor facing the patient. The video signal is contemporaneous with all other data streams. Patients who are asleep will not perform the task or be videotaped.

All patients – whether awake or asleep – will undergo photography of the surgical site as well as any other aspect of the research necessary to reconstruct the electrode configurations (all patients) and/or behavioral task (awake, frameless DBS patients only).

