### **Photography and videography**

Awake, frameless DBS patients will be videotaped during performance of the task. We will also photograph the surgical site as well as any other aspect of the subject's research participation that will help us correlate the patient's condition with the ECoG data. In all, the videos and photos we record can include the full face, upper body, arms, legs and surgical site. Asleep patients will not undergo video recording, however we will still photograph the surgical site in these patients. Photography and videography carry a risk of loss of privacy. Photos and videos will be stored on a secure server. Only approved study personnel will have access to these files.

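### Aim 2 asks about tDCS effects without movement, but the plan records no movement in awake patients wearing a headframe

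*Combined protocol and SAP*

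**What the plan says.** Section 1.0 puts the Aim 2 question as "Does tDCS modulate motor cortical oscillations in the absence of movement", and the Aim 2 hypothesis repeats the no-movement condition. The population is given there too: "In patients undergoing framed DBS (either awake or asleep), cortical oscillatory changes will be recorded during application of tDCS".

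Section 3.0 (Procedure steps) separates this group from Aim 1 by the task alone: "the task will not be performed if the patient is awake but has a stereotactic headframe on or is asleep under general anesthesia".

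Two movement measures are planned:

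- **Video.** Section 13.0 (Photography and videography) says "Awake, frameless DBS patients will be videotaped during performance of the task". Section 9.0, Step 3 adds "Patients who are asleep will not perform the task or be videotaped". Neither section mentions filming awake framed patients.
- **Hand controller.** Section 9.0, Step 2 describes "a hand controller that is held by the patient and tracked in three-dimensional space, serving as a marker of upper extremity movement". It belongs to the virtual reality system, which is described only for awake frameless patients.

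On why movement matters, section 1.0 calls PD "a movement disorder characterized by resting tremor", and section 2.0 treats beta and broadband gamma as correlates of movement.

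**The concern.** Not performing a task is not the same as not moving. A patient under general anaesthesia can reasonably be taken as still. An awake patient with PD or ET in a headframe cannot: tremor may be present, and nothing in the plan records whether it is, or whether it changes when the current is switched on.

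The two Aim 2 outcomes are the bands that the protocol links to movement. For the reaching task it recognises the problem, asking for natural speed so that movement speed and force do not confound beta and gamma (section 9.0, Step 3). Aim 2 has no equivalent safeguard for its awake patients.

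At stake is the interpretation of Aim 2 in this subgroup. If beta falls during stimulation, the data could not show whether tDCS acted on a resting cortex or whether the patient moved or trembled more. If tDCS itself altered tremor, the cortical change would still be caused by tDCS, but it would not answer the question Aim 2 asks. Recordings not made during surgery cannot be recovered later.

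**Working it through.** **1. Is movement recorded by any other route in awake framed patients?**

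- Video: tied to the task in awake frameless patients (sections 3.0, 9.0 Step 3, 13.0).
- Hand controller: part of the virtual reality set-up for awake frameless patients (section 9.0, Step 2).
- Other signals: section 10.0 lists sECoG, tDCS and goggle outputs, photography and videography, and imaging. No EMG, accelerometer or tremor rating during recording is listed.
- Clinical scales: section 10.0 collects ratings before and after surgery, not during stimulation.
- Photographs: taken in all patients (section 9.0, Step 3), but stills do not show movement over time.
- Instruction to rest: given only within the task (section 9.0, Step 3).

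No concurrent measure is planned for this subgroup.

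**2. When would this bias the result?** Let p_on and p_off be the fractions of epochs with movement with stimulation on and off, and m the change in log10 beta power in such an epoch. With no direct tDCS effect,

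mean on-minus-off difference = (p_on − p_off) × m.

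If p_on = p_off the difference is zero, so stable tremor largely cancels. If p_on is above p_off, with m negative, beta appears to fall. If tDCS reduced tremor, the sign would reverse.

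**3. A hypothetical size.** The protocol gives no value of m for spontaneous movement or tremor. The only figures available are the preparation-phase beta values in section 5.0: PD −0.31 and ET −0.071 log10 units. Used as a stand-in range:

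- 10% more movement epochs: 0.10 × −0.071 = −0.007; 0.10 × −0.31 = −0.031.
- 20% more: 0.20 × −0.071 = −0.014; 0.20 × −0.31 = −0.062.

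As power ratios, 10^−0.0071 = 0.984, 10^−0.0142 = 0.968, 10^−0.031 = 0.931 and 10^−0.062 = 0.867: about 2%, 3%, 7% and 13% lower. These assume that log power is averaged. Averaging raw power first gives (p_on − p_off) × (1 − 10^m): 0.10 × 0.510 = 5% and 0.20 × 0.510 = 10% for PD; 0.10 × 0.151 = 1.5% and 0.20 × 0.151 = 3% for ET. The protocol states no averaging rule.

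**4. Against the planning difference.** Section 5.0 plans on 0.24 with SD 0.19 (0.06 × √10 = 0.19, the PD group) and an intra-class correlation of 0.7. The shifts above are 0.0071/0.24 = 3% to 0.062/0.24 = 26% of that difference. If the same SD and correlation applied to a paired on-off contrast, the SD of the difference would be 0.19 × √(2 × 0.3) = 0.147. In a two-sided 5% paired t-test with no direct tDCS effect, a shift of 0.06 (25% of 0.24) would be declared significant in 11% of studies with 5 awake framed patients and 21% with 10. A shift of 0.024 (10% of 0.24) would give 6% and 7.5%. The protocol does not state the number of such patients, and it specifies no test for Aim 2.

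**The case against.** **The phrase may simply mean no task.** Section 1.0 elsewhere describes asleep patients as not engaged in a motor task, so the no-movement wording could be shorthand. This has force, and rewording is a legitimate fallback. But both the Aim 2 question and its hypothesis refer to movement, and a conclusion stated in those words would go beyond the data.

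**Video is not forbidden.** This stands. Only asleep patients are expressly excluded from filming, and section 10.0 lists videography among the data for enrolled subjects. A reader might infer that movement in awake framed patients could never be detected. The documents support only that recording it is not planned.

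**The effect may be small.** This also stands. The values used come from preparation for a cued reach, not from tremor at rest, and the beta and gamma changes in section 2.0 are described for cued tasks. Only a difference in movement between conditions matters, so it cannot be said that every awake framed patient is affected.

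**The mechanism is assumed.** Section 13.0 cites tingling or burning at 70.6%, and a reader might infer that these sensations make patients move when stimulation starts. The section describes sensations at the electrode site and says nothing about limb movement.

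**The awake-asleep comparison.** A reader might infer that it is biased in a known direction. Section 1.0 does not say that its awake side is the framed subgroup; frameless patients have video and a controller.

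**Conclusion.** The gap holds for awake framed patients. The plan defines Aim 2 by a condition that it does not measure in this subgroup, so the plan as written cannot support a no-movement conclusion there. Patients under general anaesthesia are not affected in the same way, but no analysis is described that separates the two groups.

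The size and direction of any bias are unknown. The range of −0.007 to −0.062 log10 units assumes 10% to 20% more movement epochs with stimulation on, each with a response between the ET and PD preparation values. A reader might take the PD value alone, about a 51% fall in power (10^−0.31 = 0.49), as the likely error. The documents do not support that: it would need movement in every stimulation-on epoch and none in the off epochs, at a response measured in a different setting.

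Confidence is high that the measurement is missing and low on how much that would change the result. The change should be made because it is cheap and has to be in place before the recordings are taken.

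**What to change.** In sections 3.0 (Procedure steps), 9.0 (Step 3) and 13.0 (Photography and videography):

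- Extend the existing webcam video, already recorded in time with the other data streams, to awake framed patients for the whole sECoG recording, with the limbs in view.
- Include a stimulation-off baseline, which is not described for Aim 2 at present, and instruct these patients to rest quietly.

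In the Aim 2 analysis:

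- Report the proportion of epochs with movement or tremor by stimulation condition.
- Report awake and anaesthetised patients separately.
- Add a sensitivity analysis that excludes or adjusts for movement epochs. Excluding all tremor epochs should not be the primary rule: it could remove most of the data in tremor-dominant patients, and it selects on something that stimulation may change.

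If filming is not feasible, limit the no-movement conclusion to anaesthetised patients, and reword the aim for awake framed patients so that it refers to the motor task not being performed.

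The cost is a small protocol and consent amendment, some time to review video, and minor set-up within the 20-minute limit, which already covers setting up and removing equipment.

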## 2.0 Background

### Understanding tDCS effect through synchronized cortical oscillations

Transcranial direct current stimulation (tDCS) has been shown to transiently improve deficits during physical rehabilitation sessions in small studies of patients with motor dysfunction, such as PD and chronic stroke. Nevertheless, widespread clinical use of tDCS has not gained significant traction because several large multi-center, randomized, sham-controlled trials have not yet shown consistent effects across these populations. One plausible explanation is incomplete understanding of tDCS effect on motor networks, in part due to lack of direct access to in vivo recordings to inform its mechanism. In other models with access to in vivo cortical recordings, such as epilepsy, cortical beta (13-30 Hz) and broadband gamma (70-200 Hz) oscillations have been shown to play critical roles during voluntary movement. In cued motor tasks, the spectral power of cortical beta decreases, termed event-related desynchronization (ERD, associated with release of movement inhibition), while broadband gamma power increases, or undergoes event-related synchronization (ERS, reflecting cortical population spiking). In both health and disease states these frequency bands are important neurophysiological correlates of movement and can be detected in functionally connected areas throughout the sensorimotor cortex, including premotor cortex (PreMC), primary motor cortex (PriMC) and primary sensory cortex (PSC). Several authors have attempted to record oscillatory patterns with scalp EEG in relation to tDCS activation in healthy subjects, however no consistent theme has emerged and the results are often contradictory. In the only study of its kind, Jang and colleagues used subdural electrocorticography (sECoG) in anesthetized beagles during tDCS and observed broad-spectrum but nonspecific oscillatory changes. A recent systematic review underscored the lack of understanding of the physiological mechanism underlying motor cortical influence of tDCS in patients with motor dysfunction.

In summary, motor cortical oscillatory changes related to movement can serve as a powerful cortical biomarker of intended or actual motor activity, as shown in our previous work. tDCS, which delivers current noninvasively to cortical targets, has the potential to expand the options for treatment of motor deficits in many clinical populations. Combining sECoG with tDCS will allow a detailed characterization of motor cortical oscillation changes during movement in

relation to tDCS activation. The clinical standard of care evaluation and treatment for movement disorders will not be modified by this research. The surgery for movement disorders will not be hampered by the research procedures (application of tDCS and the sECoG electrode) as explained in detail in section 3.0 below. Our previous data on PD provides an important proof of concept to demonstrate that tDCS might possibly work by modulating oscillations to improve motor symptoms.

